### **13.1.4 Recording of AEs**

Investigators must record in detail all AEs (signs and symptoms) that have occurred in the study on the corresponding CRFs, including those reported by the patients voluntarily or observed during or after the treatment.

The records of the AEs shall describe the following:

- (1) Name.
- (2) Date of occurrence.
- (3) Date of resolution/relief (duration).
- (4) Determination of the severity of the AE.
- (5) Investigators must make judgment on the possible causality between the AEs and the investigational device or surgery.
- (6) Actions taken (if any).
- (7) Outcome.

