## 5. Objective and Content of Clinical Trial

### 5.1 Objective

The clinical safety and efficacy of the JuggerStitch™ in repair of meniscal tears are assessed by comparing the clinical data of the Fast-Fix 360.

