#### 5.2.1 Secondary Endpoints

- (1) Immediate device success rate postoperatively;
- (2) Lysholm Knee Score at postoperative 3 months and 12 months;
- (3) Tegner Activity Score at postoperative 3 months, 6 months and 12 months;
- (4) Visual analogue scale (VAS) score for pain at postoperative 3 months, 6 months and 12 months;
- (5) Meniscus healing evaluated by Magnetic Resonance Imaging (MRI) scans at postoperative 6 months and 12 months;
- (6) Device-related adverse event rate.

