#### Statistical analysis method for safety:

The incidence of adverse events such as pain, device loosening or detachment, and retear occurring during surgery, as well as immediately, at 3 months, 6 months and 12 months postoperatively will be counted.

The type and frequency of adverse events, and their relationship with the investigational medical device will be described. Cases where the clinical trial is suspended due to adverse events and severe or serious adverse events will be specifically noted.

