## 13. Provisions on Reporting of AEs and DDs

### 13.1 Adverse event (AE)

#### 13.1.1 Definition of AE

*Adverse Event (AE):*

An adverse event is any untoward medical occurrence, unintended disease or injury, or untoward clinical signs (including abnormal laboratory findings) in participants, users or other persons, whether or not related to the investigational medical device.

**Note 1:** This definition includes events related to the investigational medical device or the comparator.

**Note 2:** This definition includes events related to the procedures involved.

**Note 3:** For users or other persons, this definition is restricted to events related to investigational medical devices.

*Serious Adverse Event (SAE):*

A Serious Adverse Event is any adverse event that:

- a. led to death.
- b. led to serious deterioration in the health of the participant, that either resulted in:
  1. a life-threatening illness or injury, or
  2. a permanent impairment of a body structure or a body function, or
  3. in-patient or prolonged hospitalization, or
  4. medical or surgical intervention to prevent life-threatening illness or injury or permanent impairment to a body structure or a body function.
- c. led to fetal distress, fetal death or a congenital abnormality or birth defect.

**Note:** Planned hospitalization for a pre-existing condition, or a procedure required by the protocol, without serious deterioration in health, is not considered a serious adverse event.

*Adverse Device Effect (ADE):*

An Adverse Device Effect is an adverse event related to the use of an investigational medical device.

**Note 1:** This definition includes adverse events resulting from insufficient or inadequate instructions for use, deployment implantation, installation, or operation, or any malfunction of the medical device.

**Note 2:** This definition includes any event resulting from use error or from intentional misuse of the medical device.

*Serious Adverse Device Effect (SADE):*

A Serious Adverse Device Effect is an adverse device effect that has resulted in any of the consequences characteristic of a serious adverse event.

*Device Deficiency*

A Device Deficiency is defined as an inadequacy of a medical device with respect to its identity, quality, durability, reliability, safety or performance.

**Note:** Device Deficiencies include malfunctions, use errors, and inadequate labeling.

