#### Reporting and Documentation of Adverse Events and Adverse Device Effects

Adverse Events and Adverse Device Effects (Table 1) have to be documented on the Adverse Event Report form over the whole time of the investigation including information on the date of onset, treatment and resolution, as well as assessment of both the seriousness and the relationship to the study device. Adverse Events that are deemed unrelated to the investigational device, the study protocol or procedure by the investigator will not be reported or followed. Further, the outcome of complications has to be documented and any changes in outcome are to be updated during the course of the study. In case of early termination of the study, further follow-up of the patient shall proceed according to the hospital's standard procedure.

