#### Reporting and Documentation of Serious Adverse Events, Serious Adverse Device Effects, and Device Deficiencies

**Serious Adverse Events and Serious Adverse Device Effects** have to be **reported to the Sponsor as soon as possible**. The incidence has to be documented on the **Adverse Event Report form** over the whole time of the investigation including information on the date of onset, treatment and resolution, as well as assessment of both the seriousness and the relationship to the study device based on the evaluation of the investigator. The outcome of such complications has to be documented and any changes in outcome have to be updated during the course of the study. In case of early termination of the study, further follow-up of the study participant shall proceed according to the hospital's standard procedure.

**Device Deficiencies** that did not lead to an adverse event but **could have led** to a medical occurrence if suitable actions had not been taken, if intervention had not been made or if circumstances had been less fortunate shall be **reported to the Sponsor as soon as possible**, as well.

The **Investigator** is responsible for reporting all SAEs, SADEs and Device Deficiencies that could have led to a SADE to the Ethics Committee.

The contact information is as follows:

- Name of the sponsor: ZIMMER (Shanghai) Medical International Trading Co., Ltd.
- Address of the sponsor: [name]
- Contact of the sponsor: [name]

- Contact information of the sponsor: [name]

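### Device-relatedness is worded inconsistently and, read literally, leaves out the control device, so the Fast-Fix 360 value of the device-related adverse event rate is not unambiguously defined

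*Combined protocol and SAP*

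**What the plan says.** Section 5.1 makes safety comparative: safety and efficacy "are assessed by comparing the clinical data of the Fast-Fix 360". Item 6 in the secondary endpoint list (5.2.1) is "Device-related adverse event rate". It names no device and gives no definition or denominator.

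The Synopsis names JuggerStitch as the investigational device and Fast-Fix 360 as the control device. The text on relatedness then divides.

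**Text that refers to the investigational device**
- 13.1.1, Adverse Device Effect: "An Adverse Device Effect is an adverse event related to the use of an investigational medical device". The serious version of the term is built on this one.
- 13.1.4, item 5: "Investigators must make judgment on the possible causality between the AEs and the investigational device or surgery".
- 7.1.2, safety analysis: the type and frequency of events and "their relationship with the investigational medical device will be described".
- 13.4, non-reporting rule: an event that the investigator does not link to the investigational device, the protocol or the procedure is neither reported nor followed.

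**Text that can reach the control device**
- 13.1.1, Note 1 to the adverse event definition: "This definition includes events related to the investigational medical device or the comparator".
- 13.4, adverse events: the report form carries "assessment of both the seriousness and the relationship to the study device".
- 13.4, serious events: "relationship to the study device based on the evaluation of the investigator".
- 13.1.3 also uses the term study device, when it defines device removal as an outcome.

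The documents do not define study device.

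**The concern.** A device-related rate can be compared between arms only if each event is judged against the device that the subject received. Four passages, including the one that instructs the investigator and the one that sets the analysis, refer to the investigational device. Note 1 in 13.1.1 treats that device and the comparator as two different things, and the Adverse Device Effect definition in the same section then omits the comparator.

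Two things are at stake. First, endpoint 6 may be zero in the control arm by construction, or may follow different rules at different sites. A literal zero would look like a safety signal against JuggerStitch even if the two devices were equally safe. Second, the non-reporting rule in 13.4 could remove non-serious events caused by Fast-Fix 360 from the report form, while 13.1.4 and item 13 of section 20.2 require all adverse events to be recorded.

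**Working it through.** The plan has no figure of its own to reproduce here. It states no expected device-related rate, no safety margin and no safety power. The sample size in 7.2.1 rests on the Lysholm score alone. The check is therefore to follow one event through the text.

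**Test case (hypothetical):** a non-serious event in a control subject, caused by Fast-Fix 360.

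| Step | Section | Literal reading | Study device read as the device used |
|---|---|---|---|
| Is it an adverse event? | 13.1.1, Note 1 | Yes | Yes |
| Is it an Adverse Device Effect? | 13.1.1 | No | No; the definition still names the investigational device |
| Causality item | 13.1.4, item 5 | Not related to the investigational device; possibly related to surgery | Unchanged; the control device is not named |
| Relationship on the report form | 13.4 | Not related, if the term means JuggerStitch | Related |
| Does it survive the non-reporting rule? | 13.4 | Only if linked to procedure or protocol | The same; this rule names the investigational device |
| Relationship in the analysis | 7.1.2 | None | None as written, unless the analyst substitutes the report form item |
| Does it count in endpoint 6? | 5.2.1 | No | Yes, if the report form item is used |

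The same event in a JuggerStitch subject counts under both readings. The difference between the arms therefore comes from the wording and not from the devices.

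**Illustration of scale**

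Inputs: 47 subjects per arm (6.1.5.7); a true device-related rate *p*, equal in both arms, which is an **assumption** because the documents give none; and *f*, the share of control subjects at sites that apply the literal reading, which is unknown and lies between 0 and 1.

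- Expected subjects with a device-related event, JuggerStitch: 47 × *p*
- Expected count, Fast-Fix 360: 47 × *p* × (1 − *f*)
- Spurious difference in rates: *p* − *p*(1 − *f*) = *p* × *f*

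| Assumed *p* | JuggerStitch | Fast-Fix 360, *f* = 1 | Fast-Fix 360, *f* = 0 |
|---|---|---|---|
| 5% | 47 × 0.05 = 2.35 | 0 | 2.35 |
| 10% | 47 × 0.10 = 4.7 | 0 | 4.7 |
| 20% | 47 × 0.20 = 9.4 | 0 | 9.4 |

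With five sites and an undefined term, *f* may lie anywhere between these limits, and the data may not show where.

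**What does not depend on device attribution.** Section 6.1.7.1 lists all adverse events and surgery-related events as safety parameters. Section 7.1.2 counts pain, loosening or detachment, and retear without asking for a cause. These can be compared between arms, on two conditions: that the 13.4 rule does not filter events differently by arm, and that the Safety Set in 7.9 is not read literally, since it requires use of the investigational device and would then drop control subjects.

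**The case against.** The strongest reply is that the protocol uses investigational device loosely for the repair device in either arm. Section 6.1.4, headed as the method for the investigational device, contains the full Fast-Fix 360 technique. The Full Analysis Set in 7.9 is described as intention-to-treat yet requires use of the investigational device, which makes sense for a two-group comparison only if the term covers both products. The two descriptions of what the report form must carry say study device, and Note 1 brings comparator-related events into the adverse event definition. On this view sites would judge each event against the device implanted.

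Much of this stands. A reader might infer that relatedness is judged only against JuggerStitch throughout. The documents do not support that, because 13.4 twice asks about the study device. A reader might also infer that the adverse event form has no category for the control device. The form is not among the documents, so its fields cannot be known.

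The reply does not settle the matter. The Synopsis and Note 1 separate the two devices, and 13.4 uses both terms in one paragraph without defining either. Loose usage explains how the text arose but does not tell a site which reading to apply.

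It can also be said that 13.1.4 and 13.4 govern different records, the case report form and the report to the sponsor, so that both can hold. The protocol does not say so, and the 13.4 subsection covers documentation as well as reporting. In addition, many control-device events may be linked to the procedure or the protocol and so survive the rule. That limits the loss but does not restore their count as device-related.

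**Conclusion.** The concern holds as an inconsistency with a definite direction of bias. The control-arm value of endpoint 6 is not unambiguously defined: it is zero under the literal reading and dependent on site interpretation otherwise. Non-serious events caused by Fast-Fix 360 and not linked to procedure or protocol may go unreported, contrary to 13.1.4.

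A reader might go further and conclude that the comparative safety objective cannot be answered, or that no valid control-arm rate could exist. Neither follows. The incidence of all adverse events, surgery-related events and the named complications can still be compared, subject to the 13.4 rule and the 7.9 wording. A valid control-arm rate is also possible if every site reads study device as the device used.

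One secondary safety endpoint is biased or undefined. The primary endpoint, the sample size and every other figure in the plan are unaffected. The counts above (about 2.4 to 9.4 expected control events lost) rest on assumed rates of 5% to 20%, equal in the two arms, and on the literal reading being applied throughout. They show scale and are not a prediction. The change is worth making because the wording favours one arm on a named endpoint and the repair is cheap.

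**What to change.** 1. In 7.1.2 (safety analysis), 13.1.1 (Adverse Device Effect and its serious form), 13.1.4 item 5 and 13.4, replace the reference to the investigational device with *the meniscal repair device used in that subject (JuggerStitch or Fast-Fix 360)*. Use the same phrase where 13.4 now says study device.
2. Reconcile the non-reporting rule in 13.4 with the requirement in 13.1.4 to record all adverse events, so that events are captured in the same way in both arms.
3. Have the investigator judge causality to the device and to the procedure separately, in both arms.
4. Define endpoint 6 as the proportion of subjects with at least one event related to their own device, reported by arm. A between-arm difference with a 95% confidence interval would be useful but is optional, since the plan describes relatedness and does not test it.
5. Align the Safety Set in 7.9 so that it plainly includes subjects treated with Fast-Fix 360. This step alone would not repair the causality wording.

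Cost: wording changes in the sections named and one case report form label. No added visits, subjects or assessments.

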### **13.3 Device deficiencies (DDs)**

#### Device Deficiency

A Device Deficiency is defined as an inadequacy of a medical device with respect to its identity, quality, durability, reliability, safety or performance.

**Note:** Device Deficiencies include malfunctions, use errors, and inadequate labeling.

It is important to document in the study also all device deficiencies that could have led to a medical occurrence but did not lead to an adverse event.

### 13.4 Safety Management – Medical Events/Adverse Events

Adverse events are required to be reported on the **Adverse Event Report Form**. The completed **Adverse Event Report Form** must be submitted to the Sponsor in a timely manner. The Investigator or Designee will also promptly provide the Sponsor with any additional requested information required for the Sponsor to comply with regulatory requirements. If applicable per their reporting requirements, the Investigator or Designee will also report applicable adverse event(s) to their EC.

The following definitions are from ISO 14155:2011.

#### Reporting and Documentation of Adverse Events and Adverse Device Effects

Adverse Events and Adverse Device Effects (Table 1) have to be documented on the Adverse Event Report form over the whole time of the investigation including information on the date of onset, treatment and resolution, as well as assessment of both the seriousness and the relationship to the study device. Adverse Events that are deemed unrelated to the investigational device, the study protocol or procedure by the investigator will not be reported or followed. Further, the outcome of complications has to be documented and any changes in outcome are to be updated during the course of the study. In case of early termination of the study, further follow-up of the patient shall proceed according to the hospital's standard procedure.

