## 6.1.7 Safety evaluation approach

### 6.1.7.1 Description of safety parameters

Safety parameters include all adverse events that occur during surgery and follow-up period, surgery-related adverse events, and device-related adverse events (MRI results at postoperative 12 months will be analyzed separately in the form of a list). See the Evaluation and Report of Adverse Events for details.

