### 6.1.7.2 Method and time selection for evaluating, recording and analyzing safety parameters

The adverse events that occur during surgery and at postoperative 1 month, 3 months, 6 months and 12 months will be recorded in detail, and evaluated and reported in accordance with the Evaluation and Report Procedure of Adverse Events.

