- (10) When an unexpected AE of the investigational medical device is discovered in the clinical trial, the investigators should work with the sponsor to modify the relevant content of the ICF, and submit to the ethics committee for review in accordance with relevant working procedures, and should ask the affected subjects or their guardians to confirm and re-sign the modified ICF after obtaining approval.
- (11) Investigators should be responsible for making medical decisions related to the clinical trial, and in the event of AEs related to the clinical trial, the clinical trial institutions and investigators should ensure that the subjects are provided with adequate and timely treatment and management.
- (12) In the event of SAEs in the clinical trial, investigators should take appropriate measures to treat the subjects immediately, and at the same time, report in writing to the medical device clinical trial management department of their respective clinical trial institution, which should then notify the sponsor in writing. Adverse events are required to be reported on the Adverse Event Report Form. The completed Adverse Event Report Form must be submitted to the Sponsor in a timely manner. The Investigator or Designee will also promptly provide the Sponsor with any additional requested information required for the Sponsor to comply with regulatory requirements. If applicable per their reporting requirements, the Investigator or Designee will also report applicable adverse event(s) to their EC. The Investigator is responsible for reporting all SAEs, SADEs and Device Deficiencies that could have led to a SADE to the Ethics Committee.
- (13) Investigators should record all AEs that occur and MDDs discovered during the clinical trial, and work with the sponsor to analyze the cause of the events to prepare a written analysis report where opinions

on continuation, suspension or termination of the trial should be proposed, to submit to the ethics committee for review through the medical device clinical trial management department of the respective clinical trial institution.

- (14) Investigators should ensure that the clinical trial data is recorded into the CRF accurately, completely, clearly and in a timely manner.
- (15) The clinical trial institutions and investigators should ensure that the data, documents and records formed during the clinical trial are authentic, accurate, clear and secure.

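### Section 13.4 drops adverse events judged unrelated from reporting and follow-up, while the rest of the protocol sets no such filter

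*Combined protocol and SAP*

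**What the plan says.** The restricting sentence is in section 13.4, under the heading on reporting and documentation of AEs and adverse device effects: "Adverse Events that are deemed unrelated to the investigational device, the study protocol or procedure by the investigator will not be reported or followed". The sentence before it, in the same paragraph, says that AEs and adverse device effects "have to be documented on the Adverse Event Report form over the whole time of the investigation", with seriousness and relationship to the study device assessed on that form.

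Other places set no relatedness condition:

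- Section 13.4, opening: "Adverse events are required to be reported on the" Adverse Event Report Form, which then goes to the sponsor.
- Section 6.1.7.1: "Safety parameters include all adverse events that occur during surgery and follow-up period, surgery-related adverse events, and device-related adverse events".
- Section 6.1.7.2: AEs during surgery and follow-up "will be recorded in detail, and evaluated and reported in accordance with the Evaluation and Report Procedure of Adverse Events".
- Section 20.2(12): "Adverse events are required to be reported on the Adverse Event Report Form".
- Section 20.2(13): "Investigators should record all AEs that occur and MDDs discovered during the clinical trial". Section 13.1.4 likewise requires every AE to be entered on the case report form (CRF).
- Section 13.1.1 defines an AE irrespective of relatedness, and its Note 1 adds: "This definition includes events related to the investigational medical device or the comparator".
- Section 13.1.2 asks for the severity of AEs, and any change in it, at each follow-up visit.

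The next sub-section of 13.4 covers serious adverse events (SAEs). It sends them to the sponsor and the Ethics Committee, again with no relatedness filter.

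**The concern.** Section 7.1.2 plans to describe the type, frequency and device relationship of AEs, and 6.1.7.1 makes the all-AE set a safety parameter. An all-AE rate is useful because it does not rest on anyone's view of cause. If events called unrelated are neither reported nor followed, the rate becomes a count of events that passed a causality judgement.

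The investigator makes that judgement. The operating surgeon knows which device was used, and the bias measures in 6.1.3 include no masking. The filter could therefore act differently between arms or between sites. Section 7.1.2 names pain, loosening or detachment, and retear among the events to be counted, and attribution of these is open to argument: 13.1.1 itself links loosening and migration of the implant to excessive activity or trauma. Once an event is called unrelated, the sponsor may have no report from which to question the call, and the event's outcome may go unrecorded.

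The sentence also names only the investigational device. How it applies to an event related to Fast-Fix 360 is not stated, although the trial's safety objective is a comparison with that device.

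**Working it through.** The plan gives no figure on this point to reproduce, so the check is mainly a comparison of texts.

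**Which sections conflict with the sentence, and how firmly**

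| Section | Duty | Relatedness filter | Conflict with the restricting sentence |
|---|---|---|---|
| 13.4, opening | Report AEs on the form and submit to the sponsor | None | Direct, on reporting |
| 13.4, preceding sentence | Document AEs on the form, with relationship assessed | None | Direct, unless read as a general rule followed by an exception |
| 6.1.7.1 | All AEs are a safety parameter | None | Direct, on the set to be analysed |
| 6.1.7.2 | Record, evaluate and report AEs | None stated | Partial: refers on to a reporting procedure |
| 13.1.2 | Record severity changes at each visit | None | Direct, on follow-up |
| 20.2(12) | Report AEs on the form | None | Weak as separate support: opens on SAEs and repeats the 13.4 opening |
| 13.1.1, 13.1.4, 20.2(13) | Define or record all AEs | None | Indirect: these concern definition or recording, not reporting |

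**Whether the sections can be reconciled as written**

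1. Suppose recording on the CRF is distinct from reporting to the sponsor. That reconciles 13.1.4 and 20.2(13) with the sentence. It does not reconcile the opening of 13.4, which concerns reporting, and it does not explain why follow-up stops.
2. Suppose 6.1.7 defers to section 13. Section 13.4 then contradicts itself, and the all-AE parameter in 6.1.7.1 has no complete reporting source. Because 6.1.7.1 lists all AEs separately from the surgery-related and device-related ones, unrelated events were evidently meant to be in the first set.
3. The form asks for an assessment of relationship. If unrelated events are not reported, that answer is hardly usable on the form.

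**Which events are exposed**

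- SAEs: covered by their own unfiltered rule. The restricting sentence does not itself exempt them, so the gap is mainly, not explicitly only, in non-serious events.
- Device-related AE rate (secondary endpoint 6): unchanged as first classified, since unrelated events lie outside it by definition. It changes only where an event would later have been reclassified.
- Lysholm score at 6 months: not affected on the text.

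**Scale**

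The planned size is 47 subjects per arm (synopsis; 6.1.5.7). If one subject's only AE is non-serious, called unrelated and not captured, the all-AE subject rate in that arm falls by

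1/47 = 0.0213, or 2.1 percentage points.

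This is the effect per affected subject. No count of such subjects is assumed, and the documents give none.

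**The case against.** The strongest reply is that the analysis may lose nothing. Section 13.1.4 puts every AE on the CRF with causality and outcome. Section 9 sends the locked electronic database to the statistician. Sections 8 and 8.3 have monitors check all CRF data against source, and the data verification plan in section 9 covers AEs. Nothing says that the section 7.1.2 summaries are built from the Adverse Event Report Form, so an event missing from that form could still be counted. This is fair and limits the likely loss. It holds only where a site follows 13.1.4 in preference to the explicit instruction in 13.4, and it does not settle the instruction to stop follow-up.

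Second, some of the cited support is thin. Section 6.1.7.2 defers to a procedure, 20.2(12) repeats the opening of 13.4, and the preceding sentence may be a rule followed by its exception. All of this stands, but the conflict with the opening of 13.4, with 6.1.7.1 and with 13.1.2 remains.

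Third, the filter removes only events unrelated to the device, the protocol and the procedure alike. An event caused by the protocol-assigned control implant can hardly be unrelated to all three. That makes the comparator point one of unclear wording, not a demonstrated loss.

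Fourth, 1/47 uses the enrolment target, whereas the safety denominator is the Safety Set, which may be smaller. It also assumes that an unreported event is uncounted. Both points are correct, which is why the figure is offered as scale only.

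Finally, the sub-section refers to a Table 1 that is not in the text supplied. Whether it bears on scope cannot be checked.

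**Conclusion.** The concern holds. Section 13.4 contains a stated rule that contradicts its own opening and the all-AE safety parameter in 6.1.7.1. If it is followed, the planned AE description is incomplete for non-serious events called unrelated, and it depends on an unmasked causality judgement. The size cannot be estimated from the documents. The conclusion rests on the text as supplied and on the assumption that at least some sites would act on the explicit instruction in 13.4. CRF recording and full source verification reduce the loss where they are followed. The matter should be fixed, but it does not threaten the primary analysis or SAE reporting.

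**What to change.** Delete the restricting sentence from 13.4. State in its place that all AEs in both arms are recorded, reported on the Adverse Event Report Form and followed, with relationship to the assigned device (JuggerStitch or Fast-Fix 360) and to the procedure recorded as attributes of each event. In 7.1.2, say that all, procedure-related and device-related AEs are summarised by arm on the Safety Set. Sections 6.1.7.1 and 7.9 already point that way.

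The cost is one deletion, one clarifying statement and some additional form entries across 94 subjects. Most of this work is already required by 6.1.7.2, 13.1.4, the opening of 13.4 and 20.2. The change should be made before data collection, because events that were never reported or followed may not be recoverable at analysis.
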